†††† All participants will be scheduled to attend V06 for blood sampling and 12-Month (post-VAC) Safety Follow-up. However, if any participants discontinue the study early, they are still to be followed for safety and are to be contacted with a Safety Follow-up call to identify the occurrence of any SAEs and AESIs that had not yet been reported. If discontinuation occurs at a scheduled visit, the participant will be provided a Memory Aid instead of a DC for SAE follow-up (including AESIs) until the Safety Follow-up call. If a participant discontinues between visits (with no Memory Aid provided yet), the participant will use the last DC received to collect information for the Safety Follow-up call. For participants who have prematurely terminated the study, the site should attempt to contact them and complete this 12-month safety follow-up (and all other scheduled safety follow-ups), except if they specified that they do not want to be contacted again and it is documented in the source document.

Table 1.3: Schedule of Activities for Supplemental Cohorts Comparator Group

Phase II/III Study, 8 Visits, 3 Telephone Calls, 2 Vaccinations, 8 Blood Sample Time points, Approximately 13 Months' Duration Per Participant

Visit (V) / Contact	Collection of information in the CRF	V01	TC1##	V02	TC2##	V03	TC3##	V04	V05	V06	V07	V08 or Safety Follow-up ####
Study timelines (Day [D])		D01	D09	D22	D30	D36	D43	D78	D134	D202	D292	D387
Time interval (days)			V01 +8 days	V01 +21 days	V02 +8 days	V02+14 days	V02+21 days	V02 +56 days	V02 +112 days	V02 +180 days	V02 +270 days	V02+365 days
Time windows (days)		N/A	[+2days]	[+3 days]	[+2 days]	[+3 days]	[+2 days]	[+9 days]	[+14 days]	[+21 days]	[+21 days]	[+21 days]
Visit procedures:												
Informed consent	X	X										
SARS-CoV-2 rapid serodiagnostic test	X	X										
Inclusion/exclusion criteria	X	X										
Collection of demographic data	X	X										
Collection of significant medical history including high risk medical conditions	X	X										
Collection of risk factors for SARS-CoV-2 exposure and COVID-19	X	X										
Physical examination*		X										

Visit (V) / Contact	Collection of information in the CRF	V01	TC1‡‡	V02	TC2‡‡	V03	TC3‡‡	V04	V05	V06	V07	V08 or Safety Follow-up ****
Study timelines (Day [D])		D01	D09	D22	D30	D36	D43	D78	D134	D202	D292	D387

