**** AESIs (serious and non-serious) will be collected throughout the study and will be communicated to the Sponsor in an expedited manner similar to the reporting of SAEs and followed-up until the end of the follow-up period or resolution, as per the assigned causality. These include: Anaphylactic reactions, Generalized convulsion, Thrombocytopenia, Thrombosis with thrombocytopenia syndrome, Myocarditis, Pericarditis, and potential immune-mediated diseases (pIMDs).

***** In case of participant discontinuation at a visit, the entire visit will be completed.

**** All participants will be scheduled to attend V08 for blood sampling and 12-Month (post-VAC2) Safety Follow-up. However, if any participants discontinue the study early, they are still to be followed for safety and are to be contacted with a Safety Follow-up call to identify the occurrence of any SAEs and AESIs that had not yet been reported. If discontinuation occurs at a scheduled visit, the participant will be provided a Memory Aid instead of a DC for SAE follow-up (including AESIs) until the Safety Follow-up call. If a participant discontinues between visits (with no Memory Aid provided yet), the participant will use the last DC received to collect information for the Safety Follow-up call. For participants who have prematurely terminated the study, the site should attempt to contact them and complete this 12-month safety follow-up (and all other scheduled safety follow-ups), except if they specified that they do not want to be contacted again and it is documented in the source document.

Table 1.4: Schedule of Activities 2 (Follow-up of COVID-19-like Illness) for the Original Phase II Cohort and all Supplemental Phase III Cohorts

Contact type	Initial Telephone Call*	CLI01	Follow-up Telephone Call†
		As soon as possible after symptom onset	30 days after symptom onset
Verify information on COVID-19-like illness, remind participant of use of pulse oximeter** and schedule appointment for collection of respiratory sample as soon as possible after illness start date‡	X		
Remind participant to complete Memory Aid or Diary Card	X		
Collection of respiratory specimen		NPXXXX§	
Collection of disease burden and health care information during COVID-19-like illness	X	X	X
Collection of treatments received during COVID-19-like illness	X	X	X

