7.2 Participant Discontinuation/Withdrawal from the Study

- A participant may withdraw from the study at any time at his/her own request or may be withdrawn at any time at the discretion of the Investigator or designee for safety, behavioral, or compliance reasons.
- The reason for withdrawal should be clearly documented in the source documents and in the CRF: Adverse Event, Lost to Follow-up, Protocol Deviation, or Withdrawal by Participant.
- The participant will be permanently discontinued both from the study intervention and from the study at that time.
- If the participant withdraws consent for disclosure of future information, the Sponsor may retain and continue to use any data collected before such a withdrawal of consent.
- If a participant withdraws consent, he/she may request destruction of any biological samples taken (unless local law required not to destroy them), and the Investigator must document this in the site study records.
- Withdrawn participants will not be replaced.

Follow-up of Discontinuations

For participants who have prematurely terminated the study, the site should attempt to contact them and complete all scheduled safety follow-ups, except if they specified that they do not want to be contacted again and it is documented in the source document.

For participants where the reason for early termination is lost to follow-up, the site will not attempt to obtain further safety information.

For participants from Original Phase II Cohort who terminate the study at D202 if they are included in the Supplemental Phase III Cohort 2.

All participants will be scheduled to attend V08 (or V07 for booster vaccine study participants) for blood sampling and 12-Month Safety Follow-up. However, if any participants discontinue the study early, they are still to be followed for safety and are to be contacted with a Safety Follow-up call to identify the occurrence of any SAEs and AESIs that had not yet been reported. If

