discontinuation occurs at a scheduled visit, the participant will be provided a Memory Aid instead of a DC for SAE follow-up (including AESIs) until the Safety Follow-up call. If a participant discontinues between visits (with no Memory Aid provided yet), the participant will use the last DC received to collect information for the Safety Follow-up call. For participants who have prematurely terminated the study, the site should attempt to contact them and complete this 12-month safety follow-up (and all other scheduled safety follow-ups), except if they specified that they do not want to be contacted again and it is documented in the source document.

See [Section 7.3](#) for definition of “lost to follow-up”.

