7.3 Lost to Follow-up

A participant will be considered lost to follow-up if he or she repeatedly fails to return for scheduled visits and is unable to be contacted by the study site.

The following actions must be taken if a participant fails to return to the site for a required study visit or cannot be contacted as planned in the SoA:

- The site must attempt to contact the participant and reschedule the missed visit as soon as possible and counsel the participant on the importance of maintaining the assigned visit schedule and ascertain whether or not the participant wishes to and/or should continue in the study.
- Before a participant is deemed lost to follow-up, the Investigator or designee must make every effort to regain contact with the participant (where possible, 3 telephone calls, text messages, or e-mails, and, if necessary, a certified letter to the participant’s last known mailing address or local equivalent methods). These contact attempts should be documented in the participant’s medical record.
- Should the participant continue to be unreachable, he/she will be considered lost to follow-up.

Discontinuation of specific sites or of the study as a whole are handled as discussed in [Appendix 10.1](#).

8 Study Assessments and Procedures

- Study procedures and their timing are summarized in the SoAs. Protocol waivers or exemptions are not allowed.
- Immediate safety concerns should be discussed with the Sponsor immediately upon occurrence or awareness to determine if the participant should continue or discontinue study intervention.
- Adherence to the study design requirements, including those specified in the SoAs, is essential and required for study conduct.
- All screening evaluations must be completed and reviewed to confirm that potential participants meet all eligibility criteria. The Investigator will maintain a screening log to record details of all participants screened and to confirm eligibility or record reasons for screening failure, as applicable.

Blood and respiratory samples will be collected as described in the SoA tables ([Section 1.3](#)).

The maximum amount of blood collected from each participant over the duration of the study, including any extra assessments that may be required, is not planned to exceed 240 mL (see [Table 8.1](#), [Table 8.2](#), and [Table 8.3](#)). Repeat or unscheduled samples may be taken for safety reasons or for technical issues with the samples.

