9.4.2.2.2 Primary - Safety

The main parameter will be described for all safety endpoints. The percentage of participants (using as denominator the number of participants) will be provided for analysis of solicited AEs, unsolicited AEs (including immediate systemic AEs within 30 minutes), SAEs, AESIs and MAAEs. The corresponding 95% CIs for the percentages will be calculated based on the Clopper-Pearson method. In the priming vaccine groups (comparator for Cohorts 1 and 2), subgroup analyses will be performed by age group (18-55 years old and \geq 56 years old), high-risk medical conditions group, and baseline SARS-CoV-2 naïve status for the main safety analyses. In the Booster Groups (in Cohorts 1 and 2), subgroup analyses will be performed by age group (18-55 years old and \geq 56 years old), high-risk medical conditions group, priming vaccine platform, and individual priming vaccine. Safety endpoints will be analyzed for each of the CoV2 preS dTM primary series dosages administered in the Original Phase II Cohort (ie, 5-10-15 μ g). The SafAS population will be used for safety analyses for the following endpoints:

- Presence and relationship of unsolicited (immediate) systemic AEs reported in the 30 minutes after each vaccination.
- Presence, time of onset, number of days of occurrence, intensity, action taken, and whether the reaction led to early termination from the study, of solicited (pre-listed in the participant's DC and CRF) injection site reactions and systemic reactions occurring up to 7 days after each vaccination.
- Presence, nature (MedDRA SOC and PT), time of onset, duration, intensity, relationship to vaccination, and whether the event led to early termination from the study of unsolicited AEs reported up to 21 days after the last vaccination.
- Presence, nature (MedDRA SOC and PT), time of onset, seriousness criteria, relationship to vaccination, outcome, and whether the event led to early termination from the study, of SAEs.
- Presence, nature (MedDRA SOC and PT), relationship to vaccination of all protocol-specified AESIs from the time of the first study vaccination throughout the study.
- Presence, nature (MedDRA SOC and PT), relationship to vaccination of MAAEs throughout the study.

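### The visit schedules and Section 7.2 give sites conflicting instructions on the 12-month safety contact for participants lost to follow-up

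*Protocol*

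**What the plan says.** **Schedules.** The Section 1.3 footnotes to Table 1.1 (Original Phase II Cohort), Table 1.2 (booster arms) and Table 1.3 (Comparator Group) carry the same rule: "For participants who have prematurely terminated the study, the site should attempt to contact them and complete this 12-month safety follow-up". The one exemption reads "except if they specified that they do not want to be contacted again and it is documented in the source document". Loss to follow-up is not named.

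**Section 7.2.** Lost to follow-up is one of the listed withdrawal reasons. Under Follow-up of Discontinuations, the general rule comes first: "the site should attempt to contact them and complete all scheduled safety follow-ups, except if they specified that they do not want to be contacted". The next paragraph adds "For participants where the reason for early termination is lost to follow-up, the site will not attempt to obtain further safety information". The section then closes by restating the rule for the 12-month contact, again exempting refusals only: "complete this 12-month safety follow-up (and all other scheduled safety follow-ups), except if they specified that they do not want to be contacted again".

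**Section 7.3.** The label applies to someone who repeatedly misses visits and cannot be contacted. Before applying it, the site must try calls, texts or e-mails and, if necessary, a certified letter. Then: "Should the participant continue to be unreachable, he/she will be considered lost to follow-up".

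**Section 9.4.2.2.2.** For SAEs, AESIs and MAAEs: "The percentage of participants (using as denominator the number of participants) will be provided". The Safety Analysis Set in Section 9.3 is randomized participants who received at least one dose, with no exclusion for loss to follow-up.

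**The concern.** A participant lost to follow-up has ended the study early. Under the schedule footnotes, the site should attempt the 12-month safety contact for that person. Under the Section 7.2 sentence, it should not. Sites may resolve this differently, so ascertainment of late events could vary by site for reasons unrelated to the participants.

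The endpoints affected are primary: Section 3 lists SAEs and AESIs throughout the study among the primary safety endpoints, and Section 8.4.1 collects SAEs to 12 months after the last vaccination. A death or hospital admission can itself make someone unreachable, so the participants for whom active seeking stops are not obviously a random subset. Table 4.1 says no independent safety board is used, so the Sponsor's Safety Team depends on what sites report.

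**Working it through.** No stated sample size, power or alpha depends on this point, so there is no plan figure to reproduce. The check is textual, followed by a bounding illustration.

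**Passages side by side, for a participant lost to follow-up who has not refused contact**

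| Place | Attempt the 12-month safety contact? |
|---|---|
| Footnotes to Tables 1.1, 1.2 and 1.3 | Yes; only a documented refusal is exempt |
| Section 7.2, general rule | Yes; only a refusal is exempt |
| Section 7.2, sentence on loss to follow-up | No |
| Section 7.2, closing restatement | Yes; only a refusal is exempt |
| Section 8.4.3 | Follow-up of a reported AE ends at loss to follow-up; silent on the 12-month contact |

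The exception for loss to follow-up therefore stands in one sentence. It is missing from all three schedules and from the restatement later in the same section. Section 8 makes adherence to the schedules a requirement of study conduct, so a site cannot simply let Section 7.2 prevail. The restatement also names V07 as the booster 12-month visit where Table 1.2 has V06, a further sign that this section was not aligned with the schedules.

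**What stops and what continues after the label.** Active seeking stops. Passive reporting continues: under Section 8.4.1, an SAE or death that the investigator learns of after discharge and considers reasonably related must be notified.

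**Illustration of scale (assumptions, not protocol figures).** Let L be the share of participants lost and f the share of their events that goes unseen. If their event risk p equals everyone else's, the reported proportion is p(1 − L) + pL(1 − f) = p(1 − Lf). The ratio of reported to true is therefore 1 − Lf.

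The only attrition figures are in Section 9.2: 3% for booster groups to 14 days, 10% for the primary vaccination group to D36, and about 15% for the Original Phase II Cohort. None is a 12-month loss rate; they serve here only as a range for L.

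| L | f = 0.5 | f = 1 |
|---|---|---|
| 3% | 1 − 0.015 = 0.985 | 1 − 0.03 = 0.97 |
| 10% | 1 − 0.05 = 0.95 | 1 − 0.10 = 0.90 |
| 15% | 1 − 0.075 = 0.925 | 1 − 0.15 = 0.85 |

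For rare events, suppose 10% of the 515 Comparator participants (about 52) were lost before any late event. The chance of missing at least one event is 1 − (1 − p)^52:

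- p = 0.5%: 23% (expected number missed 52 × 0.005 = 0.26)
- p = 1%: 41% (0.52)
- p = 2%: 65% (1.04)

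These figures describe loss to follow-up as a whole. The part attributable to the Section 7.2 sentence is L × f × g, where g is the share of otherwise unseen events that one further 12-month attempt would recover. The protocol offers nothing from which to estimate g. Since the attempt comes after the Section 7.3 efforts have failed, g is probably small.

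**The case against.** The strongest defence is that the Section 7.2 sentence is a deliberate, specific carve-out. It directly follows the general rule, and Section 8.4.3 agrees in spirit by ending AE follow-up at loss to follow-up. The footnotes mainly picture people still in touch with the site, since they describe handing over a Memory Aid or using the last diary card. This makes the carve-out a plausible intention. It does not remove the conflict, because a deliberate exception would need to appear in the three footnotes and the closing restatement, and it does not.

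Several stronger readings are tempting, and the defence is right to resist them:

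- A reader might infer that late events in these participants are never sought. Section 7.3 requires repeated failure to return and real contact efforts before the label applies, and those efforts are occasions on which an event can be learned. One missed visit does not meet the definition.
- A reader might infer that such events can never reach the pause criteria in Section 8.4. Related SAEs and deaths that become known must still be reported under Section 8.4.1.
- A reader might infer that lost participants are formally scored as event-free. Section 9.4.2.2.2 gives a denominator, not a missing-data rule, and handling of incomplete follow-up may be in the statistical analysis plan, which is not at hand.
- A reader might take the illustrated shortfalls as the bias caused by this sentence. They are the assumed effect of people being lost at all.

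**Conclusion.** The conflict is real and on the page. Three schedule footnotes and the closing restatement of Section 7.2 require an attempt at the 12-month safety contact for early terminators other than documented refusals; one sentence in Section 7.2 rules it out after loss to follow-up. If a site follows that sentence, active seeking of SAEs, AESIs and vital status ends when the label is applied, and late events on primary safety endpoints may be under-ascertained.

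The size cannot be derived from the protocol. The illustrated ratios of 0.985 to 0.85 rest on borrowed attrition rates, an assumed unseen share of one half to all, and average risk among the lost. The improvement from one further attempt would be a fraction of that shortfall, probably a small one. No hypothesis test, power or alpha statement changes. This is a cheap correction to contradictory instructions with a modest benefit for safety ascertainment. It does not show that the safety rates are materially biased.

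**What to change.** Reconcile the passages so that sites have one instruction. The preferred route is to delete the Section 7.2 sentence on loss to follow-up, or amend it so that the site makes one further attempt at the 12-month time point to obtain SAEs, AESIs and vital status, unless the participant asked not to be contacted. This agrees with what the schedules already ask for.

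If the sponsor does intend to exempt participants lost to follow-up, the exemption should instead be written into the footnotes to Tables 1.1, 1.2 and 1.3 and into the closing restatement in Section 7.2. That removes the contradiction but gives up the contact. In the same edit, align the booster 12-month visit number (V07 in Section 7.2 and Visit 7 in Section 8.4.2, against V06 in Table 1.2).

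The cost of the preferred route is one amended sentence and one extra, low-yield contact attempt per lost participant.

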2.1 Study Rationale

New, highly transmissible SARS-CoV-2 variants of concern have emerged and are spreading globally. The UK first identified a variant of concern called Alpha (B.1.1.7) which has been shown to be more transmissible and has since been detected in many other countries around the world (12) Other variants have emerged first identified in South Africa (Beta [B.1.351] variant), Brazil (Gamma [P.1]variant), and India (Delta [B.1.617] variant) and have now been detected in other countries. A key question is whether currently approved and available COVID-19 vaccines will be able to protect against infection or disease from these variants. Recent preliminary data using an adjuvanted protein sub-unit vaccine (Novavax) and the ChAdOx1 nCoV-19 vaccine (AZD1222 [Oxford University/AstraZeneca]) showed lower efficacy against mild to moderate COVID-19 in South Africa where the Beta (B.1.351) variant predominated compared to the efficacy observed for these vaccines in studies conducted in the UK (33) (34) (35). However, data from the Ad26CoV2.S vaccine (Johnson & Johnson/Janssen [J&J/Janssen]) showed efficacy against symptomatic disease in South Africa suggesting that the prototype vaccines confer protection against the Beta (B.1.351) variant. Sera from individuals immunized with prototype COVID-19 vaccines show an ability to neutralize the variants but to a lesser extent than the prototype strain. This decrease in neutralization is most notable against the Beta (B.1.351) variant which has a characteristic E484K mutation in the receptor-binding domain along with other mutations in the N-terminal domain of the S protein. These findings have led to the development of variant strain vaccines and regulatory guidance for the development of vaccines against the variant strains for products that have already demonstrated efficacy with the prototype vaccines (17). There has been particular emphasis on developing variant strain vaccines to protect against the Beta (B.1.351) variant. Ongoing evolution of SARS-CoV-2 variants, especially in light of the growing prevalence of vaccination and the selection pressure that this may exert raises the strong public health requirement for SARS-CoV-2 vaccines, including those protective against emergent variants of concern.

This Phase II/III study will assess the safety and immunogenicity of a CoV2 preS dTM-AS03 vaccine in adults 18 years of age and older. The goal of this study is to select an antigen dose adjuvanted with AS03 for further progression to a Phase III study.

This study will also assess the safety and immunogenicity of the CoV2 preS dTM-AS03 vaccine, including monovalent and bivalent formulations, for use as a universal late booster.

The data collected during this study will also support future development in other populations.

